8.5. Baseline Assessments

The follow assessments will be carried out at the baseline appointment:

Validated Patient Reported Outcome Measures (PROMs) Questionnaires:

Oxford hip score (OHS); International Hip Outcome Tool-33 (iHOT33); Hip and Groin Outcome Score (HAGOS); Pain Detect score; University of California, Los Angeles (UCLA) Activity Score; EuroQoL-5D score (EQ5D); Harris hip score (HHS)

CT scan:

CT imaging of pelvis

X-Ray:

Dynamic series of x-rays of pelvis and hip

Pregnancy test

Clinical assessment:

Examination of range of movement; examination of fixed flexion deformity; examination of leg length discrepancy

Subset of 50 participants (25 in each arm) will undergo gait analysis. These participants will be randomly selected from each study arm. Participants with comorbidities that significantly affect their gait will be excluded from gait analysis.

Assessors of all imaging, PROMs, and clinical assessment will be blinded to which arm of the trial patients were in.

8.6. Summary of Visits

Routine clinical practice will take priority and the study timetable has been drawn up to allow the study procedures to fall within current surgical waiting times. Taking part in the study, therefore, will not delay or expedite treatment. Below is a summary of what will take place at each visit:

Visit 1: Consent visit

- Scheduled within 4-6 weeks of when potential participants are initially approached
- Consent form discussed and signed
- Following this visit, participants will be randomised into one of the two study arms
- If patients decline entry into the study, they will be offered entry into the 3rd observational arm of the study

Visit 2: Baseline assessment visit

- Scheduled for soon after consent visit
- Baseline assessments (detailed in section 8.5) completed

Visit 3: Gait Analysis Visit (subset of patients only)

- Scheduled for same day as or soon after baseline assessment visit (because scheduling CT scan and gait analysis on the same day may not be possible)

Visit 4: Study intervention

- Scheduled for 6-8 weeks after the baseline assessment (Thus patients will have a wait for surgery of approximately 3 months after entry into the study, which is in line with the current surgery waiting time in the participating centres.) Participants will undergo THA surgery in accordance with their randomisation allocation.
- Operative details to be collected:

- Date of surgery
- Randomisation group
- Name of consultant in charge of care
- Grade of lead surgeon
- Grade of assistant surgeons
- Operative side
- Duration of surgery
- Estimated blood loss
- Surgical approach
- ASA grade
- Use of systemic prophylactic therapy (antibacterial and anticoagulant)
- Anaesthesia type
- Acetabular and femoral bone quality
- Whether there was an attempt to correct leg length (if so, what amount attempted and achieved)
- Occurrence of per-operative complications
- Ease of reduction
- Acetabular grafting performed
- Femoral grafting performed
- Details of hip prosthetic components used – including information from device labels
- Other comments on operation

Visit 5: 3-month post-operative visit

- Completion of PROM questionnaires
- Clinical assessment (to include full examination of hip joint and assessment of leg length discrepancy)
- Recording of dislocations, further surgeries or adverse events
- Recording of details of any other healthcare usage by the participants (for cost analysis)
- Review of medical records and recording of any significant events

Visit 6: 6-month post-operative visit

- Completion of PROM questionnaires
- Clinical assessment (to include full examination of hip joint and assessment of leg length discrepancy)
- Recording of dislocations, further surgeries or adverse events
- Recording of details of any other healthcare usage by the participants (for cost analysis)
- Standardised anteroposterior and lateral x-rays taken
- Review of medical records and recording of any significant events

Visit 7: 12-month post-operative visit

- Completion of PROM questionnaires
- Clinical assessment (to include full examination of hip joint and assessment of leg length discrepancy)
- Recording of dislocations, further surgeries or adverse events
- Recording of details of any other healthcare usage by the participants (for cost analysis)
- Standardised anteroposterior and lateral x-rays taken
- Gait analysis performed on the subset of 50 participants randomly selected pre-operatively

- Subset of 50 participants will undergo a post-operative CT scan. These 50 participants will be randomly selected from arm 2 (OPS arm) of the study cohort.
- Review of medical records and recording of any significant events

Completion of this visit marks the end of trial participation

Reasonable travel expenses to the hospital for the additional appointments for the study purposes will be reimbursed.

9. DESCRIPTION OF PROCEDURES

THA will be performed under general anaesthesia or spinal anaesthesia. The surgical technique will be standardised across all sites. All surgeons operating within the trial perform in excess of 60 hip arthroplasties annually. THA will be performed via anterior, antero-lateral, lateral or posterior approach. The study will use the Corin Trinity shell system for the acetabular system. The study will use all compatible Corin stem implants (MiniHip, TriFit, MetaFix and TaperFit) for the stem implant. All head and stem sizes will be included in the trial. All implants will be supplied by Corin Ltd. Pre-operatively all patients (both arms) will undergo dynamic imaging (computer tomography scanning and X-ray films) of their pelvis and hips.

Arm 1: Best practice total hip arthroplasty (THA) with conventional templating

An antero-posterior view radiograph of the pelvis (with legs positioned in 15° internal rotation) and a lateral view radiograph of the hip are required for conventional templating. The radiographs will be examined pre-operatively and appropriately sized cup and stem implants selected for each patient. Intra-operatively, the surgeon may select a different sized implant to that predicted by templating if clinically appropriate.

Arm 2: Best practice total hip arthroplasty (THA) with Corin OPS to guide templating

Patients in the intervention arm will undergo an identical total hip arthroplasty operation. The difference will be the templating procedure used to accurately align the acetabular cup.

The pre-operative dynamic imaging of patients in the OPS arm will be used to calculate the personalised target orientation of the acetabular cup in each patient. A unique physical guide is then created for each patient, which facilitates the accurate positioning of the prosthetic acetabular cup. The guide is a model that fits precisely into the acetabular fossa.

At the appropriate step during the operation, the acetabular fossa is cleared of the fat pad and remnants of the ligamentum teres. Cartilage is removed from areas within the acetabulum where the arms of the guide will sit. The guide is then placed accurately into the acetabular fossa, using guide-holding forceps. Five reference markings on the model assist with accurately locating the guide. Superomedial pressure is applied to ensure it is fully seated within the fossa and rigidly stable. An acetabular laser assembly is then attached to the back of the guide. A pelvic screw is screwed into the bone either around the acetabulum within the incision or percutaneously into the iliac crest. Once the screw is fixed rigidly, a pelvic laser assembly is attached to the back of the pelvic screw. The alignment of the pelvic screw laser is then

adjusted until the laser converges with the laser of the acetabular guide, as projected onto the operating theatre wall or ceiling. The pelvic laser is secured with a dial.

The acetabular laser assembly is then detached from the guide, and the guide is removed from the acetabulum. The pelvic laser assembly is detached from the pelvic screw. The acetabulum is reamed as per the routine technique. The pelvic laser assembly is then reattached to the back of the pelvic screw. Care is taken not to change the direction of the pelvic laser. Next, the acetabular laser assembly is connected to a magnetic impactor adaptor and attached to the back of the prosthetic acetabular cup introducer. The cup is placed in the acetabulum and the orientation is adjusted until the acetabular laser converges with the pelvic laser. The pelvic laser assembly is removed and the acetabular cup is impacted. Note that the pelvic laser assembly can be repeatedly attached and removed to assess alignment during impaction. Once the cup is fully impacted in a satisfactory position, the pelvic screw can be removed, and the operation completed as per the routine technique.

In both arms all intra-operative findings will be recorded on the operation note. Participants will be assessed post operatively by the physiotherapy and medical teams to ensure safety for discharge and when safe patients will be discharged home in line with standard routine care. After discharge, all patients will follow an identical physiotherapy regime, which will follow standard practice after total hip arthroplasty.

Patients receiving the THA operation will have either a general anaesthetic or an epidural anaesthetic. The decision of which type of anaesthetic is given is up to the clinical judgement of the anaesthetist, and will be based on the patient's overall health status. For patients undergoing epidural anaesthesia, a large sterile sheet drape will be placed vertically at the level of the patient's abdomen during surgery. This is to both (1) keep the surgical field sterile and (2) completely obstruct the patient's view of the surgical field and the surgeon, which could prove distressing to the patient during surgery. Furthermore, patients will be given strong relaxant medications during surgery, making them less aware of what is taking place. The patients who undergo epidural anaesthesia therefore will not be able to tell what type of templating is taking place, and so blinding will remain in place.

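### Section 9's assurance that patients not under general anaesthesia cannot tell their arm goes beyond its stated measures, which are not said to cover the OPS-only lasers projected on the theatre wall or ceiling

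*Combined protocol and SAP*

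**What the plan says.** Section 9 of the protocol describes the two operations and then the anaesthesia.

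- **OPS arm.** With the guide seated, the pelvic laser is "adjusted until the laser converges with the laser of the acetabular guide, as projected onto the operating theatre wall or ceiling". After reaming, the cup goes in and "the orientation is adjusted until the acetabular laser converges with the pelvic laser". The section adds that "the pelvic laser assembly can be repeatedly attached and removed to assess alignment during impaction".
- **Control arm.** Templating is described from radiographs, and no laser step is mentioned.
- **Anaesthesia.** "Patients receiving the THA operation will have either a general anaesthetic or an epidural anaesthetic", and the choice is left to the anaesthetist. For epidural patients, a vertical drape at the abdomen is to block their "view of the surgical field and the surgeon". In addition, "patients will be given strong relaxant medications during surgery, making them less aware of what is taking place".
- **Conclusion drawn.** "The patients who undergo epidural anaesthesia therefore will not be able to tell what type of templating is taking place", from which the section infers that the blind is kept.

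The opening of section 9 speaks of spinal rather than epidural anaesthesia. Because the later sentence divides all patients into general or epidural, I read the measures as meant for everyone not under general anaesthesia, and I treat the change of term as editorial.

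Sections 6 and 8.4 declare the participant to be the blinded party. Sections 8.4 and 8.5 also blind those who assess patients and images, while the surgeon and theatre staff know the allocation. Section 11.6 limits the analysis of an unblinded participant to what was collected beforehand.

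**The concern.** The assurance is absolute, and it is presented as following from two measures. One cue that belongs to the OPS operation lies outside what the first measure is said to hide. The second measure is described only as reducing awareness.

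Two things are at stake.

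- **Patient-reported outcomes.** The Oxford hip score, iHOT33, HAGOS, Pain Detect, EQ-5D and UCLA score are collected at 3, 6 and 12 months (section 5), all after surgery. A patient who believes that the newer technique was used, or was not, may answer differently. Blinding the assessors does not remove that effect, because the patient supplies the score.
- **Data retained for analysis.** If section 11.6 were applied to a patient who worked out the allocation in theatre, none of that patient's post-operative data would be used, dislocation included.

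**Working it through.** No arithmetic applies. The check is whether the stated measures reach the cue.

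| Question | What the protocol states | Result |
|---|---|---|
| Is the cue specific to one arm? | Laser convergence is described for OPS; control templating uses radiographs (section 9) | Yes |
| Where is it? | On a wall or the ceiling of the theatre (section 9) | Outside the operative field |
| Is it momentary? | Used at the guide stage, again at cup placement, with optional rechecks during impaction (section 9) | No, at least two occasions |
| Is the drape said to cover it? | It covers the field and the surgeon (section 9) | Not stated |
| Do the relaxants remove awareness? | They make patients less aware (section 9) | Reduced, not removed |
| Is there another safeguard? | Sections 8.4, 8.5, 9 and 12.2 describe no eye cover, sham laser, sedation depth that removes awareness, or check of blinding | None found |

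The premises support the statement that a patient's chance of noticing the technique is reduced. They do not support the statement that the patient cannot notice it.

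For a patient to be unblinded by this route, four things must all hold:

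1. The patient is not under general anaesthesia. The share of such patients is not given.
2. The projection is in the patient's line of sight. Patient position, drape height and the surface used are not given.
3. The patient is alert enough to notice it. Depth of sedation is not given.
4. The patient knows what a laser signifies. Section 8.3 requires a full explanation of the trial and of what it involves, but the documents do not show whether lasers are mentioned.

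With no figure for any link, neither the number of patients affected nor the size of any bias can be calculated.

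On retained data, section 11.2 promises intention to treat, and section 11.6 opens by including everyone randomised. Section 11.6 then restricts data for an unblinded participant and does not say whether that covers a patient's own discovery. The loss of dislocation data is therefore conditional on how that rule is read.

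**The case against.** The strongest reply is that the protocol has already seen the problem of awake patients and answered it with two measures used together. The drape is described as large, and the text does not say that it hides nothing else. A vertical sheet that fully conceals the surgeon may well conceal part of the wall beyond. Strong relaxants would dull whatever remained. A light on a wall means nothing to a patient who has not been told what it signifies.

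Most of this stands as a limit on the weight of the point. It does not close the gap. The ceiling is a named projection surface, and a vertical sheet at the abdomen is not described as blocking it. Reduced awareness is all that the protocol claims for the relaxants. What patients know about lasers cannot be settled from the documents in either direction.

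A reader might go further in three ways that the documents do not support.

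- **That patients would in fact be unblinded.** Nothing in the text shows that any patient would see or recognise the projection.
- **That any unblinding would fall on the OPS arm alone.** The lasers are used only there. But an awake control patient who had been told about lasers, and saw none, could also infer the allocation.
- **That the longer OPS operation measures the exposure.** Section 14 gives an average rise from 70 to 85 minutes. That is a net figure for all the added steps and is not limited to awake patients, so it does not measure time with a laser in view.

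**Conclusion.** The point holds as a gap between the assurance and the measures offered for it. It is a possible, unquantified threat to participant blinding, mainly affecting the patient-reported secondary outcomes. It merits a cheap improvement and is not a serious flaw in the design.

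A reader might infer that the primary outcome is wholly untouched. That is reasonable for expectation effects, since dislocation and re-operation for dislocation are not self-reported scores. It is not assured for data retention: under section 11.6, a recognised unblinding could remove later dislocation data for that patient.

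The conclusion rests on two readings of the text. The first is that the drape covers what it is said to cover and is not shown to cover more. The second is that the measures are meant for every patient not under general anaesthesia. If the theatre set-up already keeps the projection out of view, the practical risk disappears, and the protocol only needs to say so.

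**What to change.** In section 9, replace the assurance with a procedure, for example:

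> Every participant not under general anaesthesia, in either arm, will wear an eye cover or have a screen placed so that the walls and ceiling are out of view. The anaesthetist will agree the form used.

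Applying it in both arms means that the cover itself does not reveal the allocation. It has to be in place before surgery, because analysis cannot restore the blind once a patient has recognised the technique. Section 9 should also use one term for the non-general anaesthetic throughout.

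The cost is protocol wording plus an eye cover or screen in theatre, with no extra visit or trial assessment. The documents give no price, so low cost is my assumption. The downside is minor inconvenience to awake patients, including controls who have no laser step.

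This deals with the intra-operative visual cue only. Two other OPS-only cues would need separate handling: a pelvic screw that may be placed "percutaneously into the iliac crest", and the 12-month CT scan drawn only from OPS patients (sections 8.4 and 8.6). The change also leaves open whether section 11.6 covers a patient's own discovery.

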9.1. Discontinuation/Withdrawal of Participants from Trial Treatment

Each participant has the right to withdraw from the trial at any time. In addition, the Investigator may discontinue a participant from the trial at any time if the Investigator considers it necessary for any reason including:

- Pregnancy
- Ineligibility (either arising during the trial or retrospectively having been overlooked at screening)
- Significant protocol deviation
- Significant non-compliance with trial requirements
- An adverse event which requires revision surgery
- Withdrawal of Consent
- Loss to follow up

The reason for withdrawal will be recorded in the CRF.

If the participant is withdrawn due to an adverse event, the Investigator will arrange for follow-up visits or telephone calls until the adverse event has resolved or stabilised.

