11.2. Description of Statistical Methods

The statistical analysis is the responsibility of the NDORMS OSIRIS Trial Statistician. A full statistical analysis plan will be written and agreed by the Trial Steering Committee before any analyses are undertaken, and all reporting will follow the CONSORT reporting guidelines.

All primary analyses will follow an 'intention to treat' (ITT) principle, with all participants included in the analyses based on the treatment arm to which they were initially randomised, regardless of their compliance with the protocol.

The analysis of this study will be performed after all participants have completed their 12-month post intervention assessment. Data will also be analysed with respect to health economics.

The primary outcome of dislocation rate will be calculated in each group. Data will be examined for distribution and the most appropriate statistical test used. If the data are normally distributed, a two-sample t-test to compare groups may be the most appropriate. Multivariate linear regression analysis will be used to identify differences between the treatment groups using separate two-way comparisons (best practice THA surgical technique and templating versus best practice THA surgical technique with OPS-guided templating). The model will be adjusted for relevant baseline characteristics.

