11.5. Procedure for Accounting for Missing, Unused, and Spurious Data

Missing or spurious data will be fully investigated as to ascertain the reason. The PI will then decide whether the participant(s) whose data are missing should continue to be followed. All missing, unused or spurious data will be accounted for in any analyses

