11.6. Inclusion in Analysis

All randomised participants will be included in the analyses. If a participant is unblinded, then only information gathered on the participant prior to unblinding will be used in the analysis.

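### Sections 9.1 and 11.5 let follow-up end at the Investigator's or PI's discretion, and no rule keeps outcome collection going to 12 months as the ITT analysis needs

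*Combined protocol and SAP*

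**What the plan says.** Section 9.1 of the combined protocol and SAP is titled "Discontinuation/Withdrawal of Participants from Trial Treatment", but its text reaches further: "the Investigator may discontinue a participant from the trial at any time if the Investigator considers it necessary for any reason including" a list of grounds. These include pregnancy, ineligibility found late, protocol deviation, non-compliance and "An adverse event which requires revision surgery", besides consent withdrawal and loss to follow-up. The only contact promised afterwards applies to adverse-event withdrawals: "follow-up visits or telephone calls until the adverse event has resolved or stabilised".

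Section 11.5 deals with missing or spurious data and adds: "The PI will then decide whether the participant(s) whose data are missing should continue to be followed". It also says that such data will be investigated and accounted for, without saying how.

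Section 11.2 plans an ITT analysis by randomised arm, "regardless of their compliance with the protocol", to be run "after all participants have completed their 12-month post intervention assessment". Section 11.6 begins: "All randomised participants will be included in the analyses". Its second sentence restricts the analysis of an unblinded participant to information gathered before unblinding.

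Section 5 makes dislocation and re-operation for dislocation the primary outcome, assessed up to 12 months. Section 8.6 lists a medical-record review at each of the 3-, 6- and 12-month visits and ends participation at the last of these.

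**The concern.** The trial treatment is a single operation. Once it is done, there is no treatment left to discontinue, so leaving the trial means leaving follow-up. Late-found ineligibility, deviation and non-compliance are the cases that an ITT analysis is meant to retain, yet section 9.1 allows their follow-up to stop. The adverse-event contact rule ends at resolution or stabilisation, which may come well before 12 months. The record reviews in section 8.6 are visit items and are not said to continue after discontinuation.

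An analysis plan can only say how to handle outcomes that are absent; it does not collect them. The trial expects few events, so unseen outcomes deserve attention. Revision surgery is also both a ground for discontinuation and close to the primary outcome, so some of the loss could be selected by outcome.

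**Working it through.** **Inputs.** From section 11.1: control rate 5.0%, OPS rate 0.5%, power 0.8, 414 evaluable, 10% dropout, 460 in total (230 per arm). From section 11.3: two-sided 5%. From section 8.4: 1:1 allocation. From section 4: most dislocations are managed without revision. The documents give no frequency for the section 9.1 grounds.

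**1. The plan's own figure.** Pooled two-proportion formula, mean rate 0.0275:
n = [1.960·√(2·0.0275·0.9725) + 0.8416·√(0.05·0.95 + 0.005·0.995)]² / 0.045² = (0.4533 + 0.1928)² / 0.002025 = 206.1, so 207 per arm and 414 in total. Then 414/0.9 = 460. Both stated figures reproduce. By the same formula power is 80.2% with 207 per arm and 84.1% if all 230 per arm supply outcomes.

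**2. Expected dislocating patients at 207 per arm.** Control 207 × 0.05 = 10.35; OPS 207 × 0.005 = 1.04; together about 11.4.

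**3. Revision ground.** A patient revised for dislocation has had the dislocation and the re-operation, so both parts of the primary outcome are met. What can be lost is later events in a patient already counted, and 12-month PROMs, Harris hip score, leg length and cost. Number exposed:
- If the section 4 statement on most dislocations holds per patient (assumption), fewer than half are revised: below 5.18 + 0.52 = 5.7 patients.
- Section 4 also calls dislocation an order of magnitude commoner than registries report, and gives 1–3% against 3–15%. If registry rates approximate revisions (assumption), 1 in 10 to 1 in 3 are revised: 11.4/10 = 1.1 to 11.4/3 = 3.8 patients.

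Both figures are ceilings, because they suppose that every such patient is then discontinued. Revisions for other causes cannot be quantified from the documents.

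**4. Other grounds.** Here a first dislocation can go unseen. One expected control event needs 1/0.05 = 20 control participants discontinued before any dislocation. That is 20/230 = 8.7% of the arm, against an allowance of 23 (10%). Twenty is a minimum, since it assumes that the whole 12-month risk still lies ahead.

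**5. Sensitivity to a missed event.** Section 11.2 leaves the test open, so two are shown (207 per arm, two-sided p):

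| Control v OPS events | Fisher | Uncorrected chi-square |
|---|---|---|
| 10 v 1 | 0.011 | 0.006 |
| 9 v 1 | 0.020 | 0.010 |
| 8 v 1 | 0.037 | 0.018 |
| 7 v 1 | 0.068 | 0.032 |
| 6 v 1 | 0.122 | 0.057 |

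Exact binomial enumeration at 5% v 0.5% gives the probability of a significant result (0.776 Fisher, 0.863 chi-square) and of a result that is significant but would not be with one control event fewer (0.090 and 0.068). The shares are 11.6% and 7.9% of significant trials. They are **conditional** on one control event being missed.

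A rough unconditional illustration (assumed): if 5 control participants were discontinued immediately after surgery, the chance of losing at least one event is 1 − 0.95⁵ = 23%. Then 0.23 × 7.9% is about 2% of significant trials (chi-square), and 0.23 × 11.6% is about 2.6% (Fisher).

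**The case against.** The strongest reply is that this is an unclear clause and not a contradiction. Sections 11.2 and 11.6 settle who is analysed and in which arm. The 12-month assessment is the default, with section 9.1 as discretion around it. The PI may continue follow-up under section 11.5 as readily as stop it, and section 11.1 budgets for 10% dropout. This largely stands: the clauses allow the loss and do not require it. Still, unguided discretion is what needs correcting, and the allowance protects power only, not against loss related to outcome.

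A second reply is that the means of collection exist. Section 6 says that dislocations, further operations and healthcare visits are recorded, and section 12.2 gives the team access to enrolled patients' records without tying it to visits. This also stands in part. A reader might infer that the data would be lost beyond recovery, and that is too absolute. But neither section requires collection after discontinuation, and record access would not replace PROMs or examination findings.

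A third reply concerns the revision ground. A reader might infer that it removes primary events. Working step 3 shows that a patient revised for dislocation is already counted.

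**Conclusion.** The gap is real and worth fixing, with a small expected effect. Sections 9.1 and 11.5 allow follow-up to end in participants whom the ITT plan means to keep, and no text requires outcomes to 12 months afterwards. At risk are mainly secondary and cost data in a few patients, plus an occasional first dislocation after discontinuation on other grounds. If losses stay within the 10% allowance and are unrelated to outcome, planned power is unchanged. The expected 10 v 1 result also remains significant after one or two missed control events.

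Two stronger readings are not supported. One is that the primary result will be biased, for example because the OPS arm has more operative steps from which to deviate. The documents give no frequency and no evidence of imbalance by arm, so bias is possible but not shown. The other is that 7.9% or 11.6% of significant trials would be overturned; those shares suppose a missed control event and are not an expected effect.

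The figures rest on the protocol's 5% and 0.5% rates and on the section 4 statements holding per patient.

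**What to change.** - **Section 9.1:** state that discontinuation by the Investigator, on any listed ground or under the open any-reason wording, does not end outcome data collection unless the participant withdraws consent to data collection. Dislocation, re-operation, PROMs and healthcare use are then collected to 12 months at the planned visits or, failing that, by telephone or through the record review and access already provided in sections 8.6 and 12.2. Bring the section title and text into line.
- **Section 11.5:** replace the sentence giving the PI the decision with one that matches this rule.
- **Section 11.6:** reconcile the second sentence, so that outcomes collected this way are not discarded if the participant is unblinded.

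The cost is protocol wording in three sections and a small effort to follow a few participants. The change concerns data collection only and leaves clinical care as it is.
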